#### *Adverse events reporting*

At the beginning of any of the follow-up SMT or placebo sessions, each patient will complete an online questionnaire without the presence of the investigator, answering whether they have suffered any adverse effects that they feel could be related to the treatment received. A clinical trial identified the following adverse effects as those most commonly reported after chiropractic treatment based on lumbar SMT: muscle stiffness, increased pain, radiating discomfort, and others (Walker et al., 2013). Following the example of this study, adverse effects will be classified into these categories, in addition to indicating whether they were triggered immediately, up to 24 hours, or more than 24 hours after the previous session, whether their duration was of minutes, hours (< 24 hours), between 24 and 48 hours, or longer than 48 hours (Walker, et al., 2013), and according to their intensity (very mild, mild, moderate, severe, very severe). A 3-point increase in the NRS-11 or the reporting of moderate to severe adverse events in three consecutive visits will raise the alert and the patient will be interviewed to determine whether care should be interrupted.

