## **Independent variables**

A computer application (random-number generator) will be used to generate a randomization sequence and thus assign each patient to one of the two groups. The SMT group will receive 3 times a week for 4 weeks a session (total of 12) based on SMT of the most painful vertebral segment (see Figure 1–3). The SMT will be performed by a chiropractor with twenty years of experience in the techniques. They will be performed with the patient positioned in the lateral decubitus position, and applying a high-speed, low-amplitude force on each side of the manipulated segment, with the aim of generating at least one joint cavitation (perceptible sound). For this, the chiropractor will use a contact with the hypothenar surface or the last phalanx of the 2nd and / or 3rd fingers of the hand with the spinous process in question. In case of not perceiving a cavitation or joint movement, the SMT will be repeated once at the corresponding side. For the placebo group, the sham SMT will be performed with the patient in the same position in the lateral decubitus position, with the lower leg extended and the upper leg flexed, and an unintended force will be applied to the gluteal region (Chaibi, et al., 2015), also bilaterally (Figure 1–3). Any cavitation perceived during both real and placebo SMT will be recorded. Healthy volunteers will not receive any intervention during the same time frame of 4 weeks.

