## **Procedures**

The study will have a total estimated duration of one year, during which each patient will participate in 12 sessions divided into 3 weekly sessions for 4 weeks (see Figure 1). Once this phase of the study has been completed, patients who had been assigned to the placebo group will be offered the possibility of receiving the equivalent

“real” treatment at the MCC free of charge. Patients who received SMT may continue at their own cost. In addition, 4 weeks after the end of the study, patients will be contacted to request that they provide data on their pain intensity and disability, as described above, as well as responses to the questionnaires proposed as follow-up. Healthy volunteers will participate in two visits, baseline and follow-up after 4 weeks.

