Official Title:

Efficacy of Chiropractic Spinal Manipulative Therapy in Patients With
Primary Chronic Low Back Pain: a Mechanistic Randomized Controlled
Trial

NCT number: Not Available

Unique Protocol ID: SMTCLBP

Date: December 15th, 2021

Statistical analyses

The normal distribution of the data will be verified using the Kolmogorov-Smirnov test. Data deviating from normality will be transformed to obtain a normal distribution before being entered into the data analysis. The two main outcome variables (clinical pain intensity and disability related to low back pain) will be compared between groups (SMT vs. placebo) over time (baseline and session 12) using a mixed analysis of variance. Average pain intensity since the previous treatment visit and in the seven days prior to the initial visit will be the variable used for statistical analyses. With an exploratory objective, the secondary variables (PCS, CSI, BDI-II, GAD scores, PPTs, degree of pain widespreadness, urinary cytokine levels, number and severity of reported adverse effects, presence of leg pain, pain medication use) will be compared between groups (SMT vs placebo) over time (baseline and session 12) using another mixed analysis of variance. To test a priori hypotheses, significant effects will be decomposed using planned comparisons. For the rest of the effects, Tukey's HSD will be used for testing any pair-wise comparisons between group means.

Pearson's product-moment correlation analyses will be carried out to examine the association between primary variables and secondary variables that demonstrate significant effects between groups over time. Subsequently, two multiple regression models will be used to examine the predictors of improvement in clinical pain and disability over time in patients who have received SMT, using secondary variables with a significant association with the primary variables. The secondary variables used for this analysis will be: baseline PCS and CSI score, baseline PPTs in the primary pain region, baseline TNF- α levels, and baseline expectations of pain relief. In addition, in another

regression model, the changes (delta) in these variables (except expectations of pain relief, since it is only measured at baseline) throughout the 4 weeks of treatment will be used as predictor variables. This is done to identify the variables most associated with clinical evolution, in order to answer the mechanistic question.

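### The adverse-effect record lists no way to mark a continuing effect, so durations may be cut short or repeats counted in the exploratory adverse-effect comparison

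*Protocol*

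**What the plan says.** The protocol's section on Adverse events reporting sets the collection: "At the beginning of any of the follow-up SMT or placebo sessions, each patient will complete an online questionnaire", "answering whether they have suffered any adverse effects that they feel could be related to the treatment received". Each effect is then classed by type, onset, duration and intensity.

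- Onset: "whether they were triggered immediately, up to 24 hours, or more than 24 hours after the previous session".
- Duration: "whether their duration was of minutes, hours (< 24 hours), between 24 and 48 hours, or longer than 48 hours".

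The section states no recall window, no resolved or continuing status, no link to an earlier report, and no rule for an effect that spans two visits. It also describes an alert that depends on reports of moderate to severe events at three visits in a row.

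On timing, Procedures gives "12 sessions divided into 3 weekly sessions for 4 weeks", and Independent variables agrees. Neither names the days or a minimum spacing.

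The SAP lists "number and severity of reported adverse effects" among the variables compared between SMT and placebo, under the words "With an exploratory objective, the secondary variables". It does not define the unit of the count: episodes, reports, visits or patients.

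**The concern.** The recording scheme works for effects that begin and end between two sessions. It works less well for one that is still present when the form is completed. At that form the final duration is unknown. At the next form the reference session has moved on, so none of the three onset classes describes when the effect began.

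The protocol does not tell the patient what to do then. If the effect is reported again, nothing listed separates the repeat from a new effect of the same type, and the count may rise. If it is not reported again, the count is right but the duration class may stay too short. Different patients may do either, and the analyst could not reliably tell which.

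What is at stake is the between-arm comparison of adverse effects. If effects last longer in one arm, a count of reports mixes how many effects occurred with how long they lasted.

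**Working it through.** **Inputs from the documents.** 3 sessions a week for 4 weeks; a form at each follow-up session; three onset classes tied to the previous session; a top duration class above 48 h.

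**Step 1, schedule.** 3 × 4 = 12 sessions, which reproduces the stated total. Reading follow-up sessions as 2 to 12 gives 11 forms. The mean gap within a weekly cycle is 168 h / 3 = 56 h.

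**Step 2, gaps of 48 h or less.** Assume fixed whole-day spacing at the same hour. If all three weekly gaps were 72 h or more they would total at least 216 h, which exceeds 168 h. So every pattern has at least one gap of 48 h or less each week. Three such gaps would total at most 144 h, so no pattern has more than two.

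| Assumed days | Weekly gaps (h) | Gaps of 48 h or less, of 11 |
|---|---|---|
| Mon/Wed/Fri | 48, 48, 72 | 8 |
| Mon/Tue/Wed | 24, 24, 120 | 8 |
| Mon/Tue/Fri | 24, 72, 72 | 4 |

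Over all fixed seven-day patterns the range is 3 to 8. The 3 arises when the single short gap is the one between weeks, which occurs only 3 times.

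**Step 3, one effect followed through.** Take Mon/Wed/Fri and an effect that starts right after session 1 and lasts 7 days.

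- Form at session 2: 48 h have elapsed, so the top duration class is not yet true.
- Form at session 3: the effect has now lasted 96 h, so the top class is true. It began before session 2, so no onset class is true.
- Form at session 4: the same onset problem. Intervals touched: 3.

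**Step 4, mean reports per effect.** Assume onset right after one of sessions 1 to 11, each equally likely, Mon/Wed/Fri visits, and a report at every form whose interval the effect overlaps.

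| True duration | Forms touched, summed over 11 start sessions | Mean |
|---|---|---|
| up to 36 h | 11 | 1.00 |
| 72 h | 18 | 1.64 |
| 96 h | 21 | 1.91 |
| 168 h | 30 | 2.73 |

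**Step 5, illustrative ratio between arms.** Let the true number of episodes be equal in the two arms. A share p (SMT) or q (placebo) is long with mean count m, and the rest are short (12 h) and count once:

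R = (1 − p + p·m) / (1 − q + q·m)

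- p = 0.20, q = 0.05, 168 h: (0.80 + 0.545) / (0.95 + 0.136) = 1.24
- p = 0.30, q = 0.10, 168 h: (0.70 + 0.818) / (0.90 + 0.273) = 1.29
- p = 0.20, q = 0.05, 96 h: (0.80 + 0.382) / (0.95 + 0.095) = 1.13
- p = 0.20, q = 0.05, 72 h: (0.80 + 0.327) / (0.95 + 0.082) = 1.09
- p = q with equal durations: R = 1.00

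If only half the repeats are reported, m for 168 h falls to 1 + 0.5 × 1.727 = 1.864. The first case then becomes (0.80 + 0.373) / (0.95 + 0.093) = 1.12.

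The documents give no adverse-effect rates or durations, so p, q and the durations are assumptions.

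**The case against.** The strongest reply is that the questionnaire is not in the documents. The protocol summarises how effects will be classed, and the online form may hold more. That stands: one can say only that no such item is listed, not that the form cannot record a continuing effect.

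A reader might also infer that a lasting effect is both shortened and then counted again. The documents do not support that as a certain sequence. The top duration class is open-ended, so a patient who reports again can select it, and the long duration is then captured. A patient who does not report again creates no duplicate. Either error is possible, and neither is certain.

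Three further points carry weight.

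- The SAP does not say that reports are added over the 11 forms. It names baseline and session 12 as the time points, so the ratios above apply only if a sum over forms is what is meant.
- Both arms use the same form and schedule, and no figure in the documents shows that durations differ between them.
- Each session is a new exposure, so a per-visit count is a legitimate harms measure. The alert also relies on visit-by-visit reports.

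One reply is weaker: that consecutive reports of the same type could be matched afterwards. A matching pair might be one continuing symptom or two provoked by successive sessions, and no listed field tells them apart.

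**Conclusion.** The point holds as a gap in the recording scheme and in the SAP's definition of the count. A carried-over effect has no correct onset class. At first report after a gap of 48 h or less, an effect cannot yet be classed as longer than 48 h. This affects 8 of 11 forms on Mon/Wed/Fri and 3 to 8 across fixed whole-day patterns. Visits at different hours of the day would shift these counts somewhat.

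The illustrative ratios of about 1.1 to 1.3 are upper bounds for the durations and shares assumed. They require Mon/Wed/Fri visits, a report at every overlapping form, a sum over all forms, and a three- to fourfold difference between arms in the share of long effects. A reader might take them as evidence that the comparison will be biased against SMT. The documents do not support that, and with equal durations the ratio is 1.00.

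The point is minor. The comparison is exploratory, and neither the primary outcomes, the sample size nor the regression aim depends on it. It is still worth settling before data collection, because the link between reports cannot be reliably rebuilt later.

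**What to change.** - **Form:** add one item asking whether the effect is new or already reported at an earlier visit, and whether it is still present now. Keep the per-visit reports. For a continuing effect, update the duration class and worst intensity when it ends; one still present at session 12 stays marked as continuing.
- **SAP:** define the number of adverse effects as distinct episodes per patient, and report alongside it the number of visits with any reported effect.
- **Alert:** the sponsor should clarify how a continuing effect relates to the three-consecutive-visit alert. This review proposes no rule.

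The cost is one item on an existing online form and a sentence or two in the SAP. The downside is a slightly longer form and some uncertainty for patients over whether a symptom is new or continuing, which is a further reason to report both measures.

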### *Clinical examination variables*

During the case history taken, data on the characteristics of the patients' CLBP will be collected. Pain intensity will be the main primary outcome. Patients will evaluate the intensity of their CLBP at the current time, as well as the mean, minimum and

maximum pain throughout the preceding seven days or since the time of the previous session, once the study is underway, according to the brief pain inventory (de Andres Ares et al., 2015; Tan et al., 2004). Pain intensity will be collected via an online questionnaire without the presence of any investigator in every visit for descriptive reasons, although only the baseline and the final values will be used for statistical analyses. The other primary outcome will be the degree of disability provoked by CLBP. Upon completing the case history, patients will fill out the Oswestry low back disability index questionnaire (Alcántara-Bumbiedro et al., 2006), which will also be completed at the end of the study.

Additionally, other pain variables will be recorded at baseline for exploratory purposes: CLBP trajectory (duration and frequency) and localization. For the later, patients will draw the area affected by their pain on a tablet, using an application (Symptom Mapper) that will allow the degree of widespreadness of their pain to be calculated (Ellingsen et al., 2021). They may also indicate any pain present of less intensity outside the low back region, as any symptom of higher intensity will necessarily exclude the patient from the study. Additionally, clinicians will determine whether the CLBP is proportionate or disproportionate to the degree or nature of the injury or pathology, with a discrete or rather diffuse distribution, according to criteria that have been defined in the literature (Nijs et al., 2015; Smart, et al., 2012). A diffuse rather than a discrete distribution has been identified as a key criterion suggesting a CS phenotype (Kosek, et al., 2021; Smart, et al., 2012).

Finally, other variables will be reported such as the intake of pain medication compatible with the selection criteria, both at baseline and at the end of treatment. Similarly, whether the patient regularly smokes will be reported at baseline, since smoking has been associated with increased serum levels of pro-inflammatory cytokines.

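### Read as printed, the adverse-event alert leaves out the worst grade on the protocol's own intensity scale

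*Protocol*

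**What the plan says.** Two adjacent sentences of the protocol's Adverse events reporting section matter here.

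The first sets out how patients' reports are classified: by type, onset and duration, and "according to their intensity (very mild, mild, moderate, severe, very severe". That is five ordered grades, with very severe as its own top level.

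The second sets the alert: "A 3-point increase in the NRS-11 or the reporting of moderate to severe adverse events in three consecutive visits will raise the alert". An alert leads to an interview on whether to interrupt care; it does not stop treatment automatically.

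The reports come from the patient at the start of each follow-up session: "each patient will complete an online questionnaire without the presence of the investigator". On the schedule, the Procedures section says that "each patient will participate in 12 sessions divided into 3 weekly sessions for 4 weeks".

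The SAP (Statistical analyses) lists the number and severity of adverse effects among the exploratory variables compared between groups. It gives no alert or stopping rule. No other trigger for interrupting care appears in the documents as supplied, though some pages were removed from them.

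**The concern.** The threshold does not match the scale it is applied to. On a scale that ended at severe, the alert's wording would mean moderate and everything above. On this scale it names the third and fourth of five grades and stops short of the fifth.

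Followed to the letter, the rule has a perverse property: a patient whose adverse effects get worse can reach the interview later than one whose effects stay moderate, or not at all through this limb. The interview is the only route to interrupting care that the supplied text describes, so its trigger should include the worst grade.

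**Working it through.** There is no stated figure to reproduce. The check sets the two sentences side by side and then applies the rule to simple report sequences.

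**Step 1. Grades covered.**

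| Grade on the protocol's scale | Counted by the alert as printed | Counted by moderate or worse |
|---|---|---|
| Very mild | No | No |
| Mild | No | No |
| Moderate | Yes | Yes |
| Severe | Yes | Yes |
| Very severe | No | Yes |

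The printed limb covers 2 of 5 grades; moderate or worse covers 3 of 5.

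**Step 2. Number of reports.** There are 12 sessions, and adverse effects are reported at the start of each follow-up session, that is, sessions 2 to 12. This gives 12 − 1 = 11 reports. The earliest session at which three consecutive reports exist is session 4 (reports at sessions 2, 3 and 4).

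**Step 3. Apply the rule.** Assume one adverse effect per report. A report that does not qualify sets the running count back to zero, and the limb fires when the count reaches 3.

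| Reports at sessions 2 to 12 | As printed | Moderate or worse |
|---|---|---|
| Moderate at all 11 | Session 4 | Session 4 |
| Very severe at session 4, moderate at the other 10 | Session 7 | Session 4 |
| Severe and very severe alternating | Never | Session 4 |
| Very severe at all 11 | Never | Session 4 |

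In the second row the literal count is 1 at session 2, 2 at session 3, 0 at session 4, then 1, 2 and 3 at sessions 5, 6 and 7. The delay is 7 − 4 = 3 sessions, which at 3 sessions a week is about one week.

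These are illustrations of what the rule does, not frequencies. If a patient also reports a moderate or severe effect at the same visit as the very severe one, that visit counts and the gap closes.

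**The case against.** The strongest reply is that nobody would apply the sentence this way. The phrase is often used loosely for moderate and above, and a safety rule that responds to moderate events while deliberately disregarding worse ones is not a plausible intention. This stands as a statement of what was probably meant. It does not make the printed threshold agree with the scale one sentence earlier.

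Second, the rule has another limb, joined by *or*: "A 3-point increase in the NRS-11 or the reporting of moderate to severe adverse events". Increased pain is one of the protocol's listed adverse-effect categories, so a very severe effect of that kind may raise the alert through the pain score. This also stands, but only in part. A very severe effect with no 3-point rise in pain (stiffness, radiating discomfort or another symptom, all of which fall within the listed categories) is not caught that way.

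Third, a reader might infer something stronger: that an automated flag will skip very severe reports, or that the trial will leave patients with very severe effects unattended. The documents do not support either. They describe an online form filled in without the investigator, but no programmed flag, and they do not say who or what raises the alert. The absence of an investigator while the form is completed does not mean that the answers go unread; the form is completed at the start of a treatment session. Nothing in the section stops a clinician from acting earlier. An automated flag that skips the top grade is only what would follow if someone programmed the sentence exactly as printed.

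**Conclusion.** The point holds as a minor one: the adverse-event threshold is wrong as written. Read literally, it omits the highest of five grades. Depending on the sequence of reports, the alert then comes later (3 sessions in the worked example) or never comes through that limb.

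This rests on three things: a literal reading of the alert sentence, one adverse effect per visit in the examples, and no other rule covering very severe effects in the pages supplied. If staff read the phrase as moderate or worse, the omission disappears in practice. The documents give no basis for estimating how many patients would be affected. Sample size, power, error rates and the primary analysis are untouched.

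**What to change.** In the alert sentence of Adverse events reporting, change the adverse-event limb so that it counts adverse events graded moderate, severe or very severe, and leave the requirement of three visits in a row as it is.

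The cost is one phrase in the protocol. The intensity grade is already collected at every follow-up session, so no new data are needed. The downside is possibly a few more interviews; if the sentence was always going to be applied as moderate or worse, there would be none.

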## **Independent variables**

A computer application (random-number generator) will be used to generate a randomization sequence and thus assign each patient to one of the two groups. The SMT group will receive 3 times a week for 4 weeks a session (total of 12) based on SMT of the most painful vertebral segment (see Figure 1–3). The SMT will be performed by a chiropractor with twenty years of experience in the techniques. They will be performed with the patient positioned in the lateral decubitus position, and applying a high-speed, low-amplitude force on each side of the manipulated segment, with the aim of generating at least one joint cavitation (perceptible sound). For this, the chiropractor will use a contact with the hypothenar surface or the last phalanx of the 2nd and / or 3rd fingers of the hand with the spinous process in question. In case of not perceiving a cavitation or joint movement, the SMT will be repeated once at the corresponding side. For the placebo group, the sham SMT will be performed with the patient in the same position in the lateral decubitus position, with the lower leg extended and the upper leg flexed, and an unintended force will be applied to the gluteal region (Chaibi, et al., 2015), also bilaterally (Figure 1–3). Any cavitation perceived during both real and placebo SMT will be recorded. Healthy volunteers will not receive any intervention during the same time frame of 4 weeks.

